2.4.5 Within 90 days prior to treatment

- CT neck-pelvis or abdominal MRI needed only before cladribine. If no nodes, all subsequent imaging may be done with spleen U/S (or abdominal U/S if no spleen), including baseline for delayed rituximab
- HBsAg, HBcAB, & HCV, HIV
- Echo, stress test, PFTs
- 24hr urine protein, creatinine clearance & UPEP
- SPEP/ immunolectrophoresis, serum light chains, T3, T4

2.4.6 Within 360 days prior to treatment

- Cervical and Thoracic (C- and T-) Spine MRI to correlate the status of the BMBx with the vertebral BMA signal by MRI. May be cancelled at the discretion of the PI. Since the baseline MRI signal in a patient with marrow involvement of HCL is not expected to change significantly during the year prior to enrollment, it is not necessary to repeat the bone marrow biopsy because the MRI was obtained closer to the time of enrollment.

3 STUDY IMPLEMENTATION

3.1 STUDY DESIGN

3.1.1 Overview

This is a randomized study of cladribine with or without rituximab in HCL, along with delayed rituximab for MRD relapse. The primary objective of the study is to determine if HCL MRD differs at 6 months after cladribine according to whether or not rituximab is administered concurrently with cladribine. MRD for the primary objective is defined as positive blood FACS, bone marrow aspirate FACS, or BMBX IHC.

Two groups, including 68 patients with HCL and no prior courses of purine analog and 62 with HCL and 1 prior course of purine analog (Cohort 1), will be randomized according to the following schema showing numbers of patients. Following enrollment of the first evaluable 68 patients with no prior purine analog, 25 additional patients will be enrolled into the Cohort 2 and they will all receive rituximab and cladribine without randomization. However, the first of the 8 weekly doses of rituximab will be administered just before rather than after the 1st of the 5 daily doses of cladribine on day 1. The goal of this 25-patient non-randomized group is 1) to enable combined treatment as an outpatient due to the time saved from not randomizing, and 2) to determine if rapid reversible thrombocytopenia can be avoided by beginning the rituximab immediately before the 1st dose of cladribine, rather than immediately afterward. If after 10 of these nonrandomized patients it is evident that toxicity is higher with rituximab begun before cladribine than afterward,

the remaining 15 nonrandomized patients will be enrolled, and treated as outpatients if possible, with the rituximab begun after the 1st dose of cladribine as in the randomized patients.

A third group will be enrolled and will contain 20 HCLv patients who will not be randomized and will receive rituximab concurrently with cladribine.

3.1.2 Schema (CdA = cladribine)

Enrollment	Classic or typical (CD25+) HCL (68 + 25 patients) (0 prior courses CdA)		Classic or typical (CD25+) HCL (62 patients) (1 prior course CdA)		Variant (CD25-) HCL (20 patients)	
Randomize	34	34			31	31
Non Randomize			25			20
Begin day 1	CdA+rituximab	CdA	CdA+rituximab*	CdA+rituximab	CdA	CdA+rituximab
When MRD+	rituximab	rituximab	rituximab	rituximab	rituximab	rituximab
If still MRD+		rituximab			rituximab	

*Rituximab beginning day 1 before dose 1 of cladribine (CdA). Otherwise CdA before rituximab on day 1.

3.1.3 Definition of MRD positivity

To determine MRD rates for the primary endpoint, incidence of MRD 6 months after cladribine, the following 3 CLIA-certified MRD tests will be used:

- Blood FACS
- Bone marrow aspirate FACS
- BMBx IHC
- For the primary endpoint, patients will be considered MRD+ if any of these 3 tests are positive. MRD relapse is defined as FACS positivity or low blood counts (ANC < 1500/uL, Plt < 100,000/uL, or Hgb < 11). Patients FACS-negative in both blood and bone marrow aspirate are considered MRD-negative regardless of blood counts. MRD in the BMBx by IHC is defined as a ratio of CD20+ cells to T cells of at least 1, and most of the CD20+ cells having morphology consistent with HCL. FACS uses multicolor flow cytometry to specifically identify and quantify HCL cells based on expression of CD19, CD22, CD20, CD11c, CD103, and restricted (lambda or kappa) light chains. Blood consensus PCR is reported as clonal rearrangement present (positive) or polyclonal rearrangement pattern present (negative). While MRD generally refers to HCL detected while a patient is in CR, patients with more than minimal disease in the BMBx, who by definition are not in CR, will also be considered MRD+ by IHC. Patients not in CR due to positive BMBx may be MRD-free by blood tests. Thus, blood MRD-free survival is usually shorter than, but could be equal to or longer than disease-free survival.

3.1.4 Additional tests for MRD

- Although FACS/PCR of bone marrow aspirate is also CLIA certified, the sensitivity and specificity of these PCR are less than FACS. Therefore, PCR results

will be reported but not included in determination of MRD for the primary endpoint.

- RQ-PCR of blood, while extremely sensitive for MRD, will not be used for protocol decisions since it is not CLIA certified and its clinical relevance needs additional study.

3.2 DRUG ADMINISTRATION

3.2.1 Cladribine

Cladribine 0.15 mg/Kg/day by 2-hour i.v. infusion days 1-5. The infusion time may be changed to 1 hour at the discretion of the PI.

3.2.2 Rituximab

Rituximab 375 mg/m² i.v. infusion every week x8, begin day 1 in half of randomized patients and in all HCLv patients, and then again in all patients at least 6 months later when HCL is detected by blood FACS. Patients who first received rituximab at least 6 months after cladribine may receive a 2nd course of rituximab at the same dose and schedule at least 6 months after the beginning of the 1st course, if and when HCL is detected again by blood FACS. When rituximab is given on the same day as cladribine (day 1), it will be given at the end of the 2-hour infusion of cladribine. In the 25 nonrandomized newly-diagnosed HCL patients beginning rituximab prior to cladribine, the 2 hour infusion of cladribine will be begin at the end of the infusion of rituximab. Actual body weight measured within 4 weeks prior to initial treatment with rituximab will be used for calculations of body surface area.

It is possible, though uncommon for HCL and HCLv to change phenotype. This would be considered a second malignancy which would require patients to be taken off-treatment. However, we feel it is justified for these patients to remain on study and continue to receive treatment despite the development a new clone (second malignancy) because they are likely to receive on-going benefit from the treatment. Thus, at the discretion of the PI, these patients may continue with treatment including delayed Rituximab if appropriate.

3.3 TREATMENT MODIFICATIONS

3.3.1 Treatment Delay

- Dosing of cladribine may be delayed up to 2 weeks, rituximab up to 12 weeks for toxicity or logistical reasons, including inability of the patient to get to clinic. The one week interval between rituximab doses may also be shortened by one day for logistical reasons.
- Patients with excessive delay or dose-limiting toxicity (DLT) are off-treatment and may be followed but not retreated.
- Infusions should be discontinued in the event of serious or life-threatening cardiac arrhythmias. Subjects who develop clinically significant arrhythmias which are not dose-limiting should undergo cardiac monitoring during and after subsequent infusions.

3.3.2 Dose-reduction

Cladribine and rituximab may not be dose-reduced. Rituximab infusion should be interrupted for severe reactions, e.g., rapid tumor lysis. Treatment of infusion-related symptoms with diphenhydramine and acetaminophen is recommended. Additional treatment with bronchodilators or IV saline may be indicated. Epinephrine, antihistamines, and corticosteroids should be available for immediate use in the event of a hypersensitivity reaction to rituximab (e.g., anaphylaxis). In most cases, the infusion can be resumed at a 50% reduction in rate (e.g., from 100mg/hr to 50mg/hr) when symptoms and laboratory abnormalities have completely resolved. Patients with severe or life-threatening anaphylaxis or hypersensitivity reaction should be removed from the study.

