2.3.2 Treatment Assignment and Randomization Procedures

Cohorts

Number	Name	Description
1	Cohort 1	Patients with HCL with (62 patients) and without (68 subjects) prior course of purine analog to be randomized between Arm 1 and Arm 2 (randomization stratified based upon prior purine analog [yes/no])
2	Cohort 2	Patients with HCL without prior course of purine analog to be directly assigned to Arm 3 (25 patients; after completion of the 68 patients without prior purine analog in Cohort 1)
3	Cohort 3	Patients with HCLv to be directly assigned to Arm 3 (20 patients)

Arms

Number	Name	Description
1	Arm 1	Cladribine + Rituximab
2	Arm 2	Cladribine (+ Rituximab after 6 months if MRD detected)
3	Arm 3	Cladribine + Rituximab (Rituximab will be administered just before rather than after the 1 st of the 5 daily doses of cladribine on day 1)

Stratifications

Name	Distinct Options	Notes

Prior purine analog	Yes No	Applies to Cohort 1 patients randomized between Arm 1 and Arm 2 only (see below).
---------------------	-----------	---

Randomization and Arm Assignment

At the time of registration, patients in Cohort 1 will be randomized between Arm 1 and Arm 2, and patients in Cohort 2 will be directly assigned to Arm 3. Patients with variant HCL (HCLv; Cohort 3) regardless of prior treatment with purine analog are assigned to Arm 3.

- Cohort 1: HCL Patients will be randomized between Arm 1 and 2. Randomization will be stratified on the basis of prior purine analog or not. There will be 68 patients randomized within the no prior purine analog stratum and 62 randomized within the 1+ prior purine analog stratum.
 - Note: The randomization for Cohort 1 will be performed by CRO personnel using randomization assignments generated by the study statistician. The Pharmacy Department will be notified of the treatment assignment once the patient is randomized.
- Cohort 2: 25 patients with no prior purine analog will be assigned directly to Arm 3 following completion of randomization of the 68 patients in the ‘no prior purine analog’ stratum in Cohort 1.
- Cohort 3: Patients with variant HCL (HCLv) regardless of prior treatment with purine analog will be enrolled in this cohort, will not be randomized and will be assigned to Arm 3.

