3.3.3 DLT criteria

Grade III-IV cladribine or rituximab related toxicity except:

- Grade 3-4 hematologic toxicity resolving in 2 weeks is not DLT.
- Grade 3 fever is not DLT.
- Grade 3 gastrointestinal toxicity for < 5 days is not considered DLT.
- Severe or life-threatening anaphylaxis or hypersensitivity reaction

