3.6 RADIATION THERAPY GUIDELINES

Radiation therapy for HCL is not permitted while on protocol. Subjects requiring radiation therapy will be considered off treatment but not off study.

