3.8.1 Criteria for removal from protocol therapy

- Voluntary patient withdrawal
- Non-compliance with treatment and tests (discretion of PI)
- The patient has received 16 infusions of rituximab
- Progressive disease after the 2nd course of rituximab
- Progression prior to finishing 2 courses of rituximab which is considered by the PI to be too rapid to treat with rituximab alone.
- Dose-limiting toxicity
- Intercurrent illness or medical circumstances making it unsafe to remain on treatment
- Radiation therapy
- Positive pregnancy test

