3.8.2 Off-Study Criteria

- Voluntary patient withdrawal
- Non-compliance at discretion of PI
- Death
- Screen failure
- Off-Study Procedure is in Section **2.3**. The reason for removing patients from study will be documented in the CRF and the medical record.

- Patients in long-term CR may become temporarily ‘lost to follow-up’ but may intend to eventually follow-up with restaging and taking them off study prematurely might greatly compromise the long-term objectives of the study. Therefore, patients may be reported as ‘lost to follow-up’ and unavailable for follow-up testing, but may continue to be followed once contact resumes. Regular communication with patients will be done to minimize this occurrence.

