Because progression of HCL following exposure to cladribine on this trial is likely to be very slow, it is extremely unlikely that any patients will have progressed within 6 months of randomization to the point of needing treatment; thus, the comparison between patients' MRD outcomes at 6 months with and without rituximab is expected to be done without any bias. In the unlikely event that a patient does receive rituximab within that time frame, or if a rare patient is given rituximab prior to demonstration of MRD, the main analysis will be done using that patient as randomized, despite receiving rituximab prior to the 6 month evaluation. This is a standard intent to treat analysis.

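### Section 3.3.2 takes patients with severe hypersensitivity off study, against Section 3.8.2; followed literally before month 6, it would lose primary MRD results almost only in Arm 1.

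*Combined protocol and SAP*

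**What the plan says.** All places are in the combined protocol and SAP.

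- **3.3.2 (Dose-reduction):** "Patients with severe or life-threatening anaphylaxis or hypersensitivity reaction should be removed from the study".
- **3.8.2 (Off-Study Criteria):** the grounds are voluntary withdrawal, non-compliance, death and screen failure. Toxicity is not among them. It adds that "The reason for removing patients from study will be documented in the CRF and the medical record".
- **3.6:** "Subjects requiring radiation therapy will be considered off treatment but not off study".
- **3.3.1:** "Patients with excessive delay or dose-limiting toxicity (DLT) are off-treatment and may be followed but not retreated".
- **3.8.1:** "Dose-limiting toxicity" is listed as a reason to leave protocol therapy.
- **3.3.3 (DLT criteria):** grade III-IV related toxicity counts, with a list of exceptions. The last bullet of that list is "Severe or life-threatening anaphylaxis or hypersensitivity reaction". The other bullets each say that the item is not DLT; this one does not.
- **2.3.2 and 3.2.2:** Arm 1 receives eight weekly rituximab doses from day 1. Arm 2 is "Cladribine (+ Rituximab after 6 months if MRD detected".
- **6.1:** the primary evaluation is at 24-28 weeks. Patients who receive rituximab early are analysed as randomised, and the section concludes: "This is a standard intent to treat analysis". Sections 1.3.2 and 3.1.3 classify a dry marrow and any positive test, but no section says how a wholly absent 6-month result is counted.

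**The concern.** An intent-to-treat comparison needs the outcome of every randomised patient, including those who stop treatment. A rule that ends study participation because of a reaction to one arm's drug makes loss of the outcome depend on treatment. All Arm 1 rituximab doses fall before the primary evaluation, and Arm 2 has none planned in that period. The wording of 3.3.2 could also reach a reaction to cladribine, so the loss would be almost, not strictly, confined to Arm 1.

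The patients concerned would have stopped rituximab early and might be more often MRD+ than the rest of Arm 1. If so, leaving them out would flatter the combination. Few MRD+ patients are expected in Arm 1, so the comparison is sensitive to single patients.

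**Working it through.** **Which passages conflict**

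- 3.3.2 against 3.8.2: a direct conflict, however the other sections are read.
- 3.3.2 against 3.6: the protocol separates the two states elsewhere, so study in 3.3.2 cannot simply be read as treatment.
- 3.3.2 against 3.3.1 and the DLT item of 3.8.1: a conflict only if the reaction is a DLT. The bullet in 3.3.3 leaves that open. Taken literally as an exception, the reaction is not a DLT and these two rules do not apply.

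**Inputs (6.1):** Fisher's exact test, one-sided 0.10; 34 per arm with MRD rates 5% vs 25% (no prior purine analog); 31 per arm with 10% vs 35% (one prior course). Expected MRD+ in Arm 1: 34 × 0.05 = 1.7 and 31 × 0.10 = 3.1.

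**Formulas.** For x MRD+ of n1 in Arm 1 and y of n2 in Arm 2, p = Σ(i ≤ x) C(n1,i)·C(n2,x+y−i)/C(n1+n2,x+y). Power is the sum of Bin(x; n1,p1)·Bin(y; n2,p2) over all (x,y) with p ≤ 0.10.

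**1. The plan's own figure.** 34 per arm: 80.6%. 31 per arm: 80.3%. The stated 80% is reproduced in both strata.

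**2. Power when Arm 1 patients are lost and left out.**

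| Stratum | None lost | One lost | Two lost |
|---|---|---|---|
| 34 per arm | 80.6% | 77.0% | 77.7% |
| 31 per arm | 80.3% | 79.0% | 79.6% |

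The figures are not monotone because the test is discrete. If one lost patient is instead counted as MRD+, power is 66.2% (34 per arm) or 69.7% (31 per arm). How a missing result is counted matters more than the lost patient.

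**3. One lost MRD+ patient, 34 per arm.**

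| Arm 2 | Patient left out | Patient restored | Crosses 0.10? |
|---|---|---|---|
| 7/34 | 2/33: p=0.082 | 3/34: p=0.152 | yes |
| 8/34 | 2/33: p=0.046 | 3/34: p=0.093 | no |
| 9/34 | 2/33: p=0.025 | 3/34: p=0.055 | no |

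**4. How often the result changes, given such a loss.** Let X ~ Bin(n−1, p1) for the remaining Arm 1 patients and Y ~ Bin(n, p2). The result changes when X/(n−1) vs Y/n has p ≤ 0.10 but (X+1)/n vs Y/n does not. Probability: 10.8% (34 per arm), 9.2% (31 per arm).

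**5. Worst-case type I error.** Both arms share one MRD rate, k MRD+ patients are removed from Arm 1, and the maximum is taken over rates from 2% to 59%.

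| k | 34 per arm | 31 per arm |
|---|---|---|
| 0 | 6.5% | 6.9% |
| 1 | 9.9% | 9.7% |
| 2 | 19.2% | 19.1% |

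**6. Rough unconditional size (assumptions).** No removal rate in HCL is given. Section 13.2.2.10 reports serious acute infusion reactions in under 1%, but in rheumatoid arthritis. Assume removal of 1-2% and that a removed patient is MRD+ at the cladribine-alone planning rate. Then P(at least one removed) × P(MRD+) × the figure in step 4 is:

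- 34 per arm: 0.289 × 0.25 × 0.108 = 0.8% to 0.497 × 0.25 × 0.108 = 1.3%.
- 31 per arm: (1 − 0.99^31 = 0.268) × 0.35 × 0.092 = 0.9% to (1 − 0.98^31 = 0.465) × 0.35 × 0.092 = 1.5%.

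If removal were 5%, 65 × 0.05 = 3.25 Arm 1 patients would be expected over both strata.

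**The case against.** The sentence stands in a section on treatment modification and may be loose wording for stopping treatment. The dedicated off-study list has no toxicity item, and Section 3.4.3 provides at least semiannual follow-up and close follow-up of grade IV toxicity. Nothing in the documents says that any patient was removed or lost a 6-month result this way. This makes a deliberate exclusion unlikely. It does not cancel the instruction in 3.3.2, and 3.4.3 allows contact by phone or email, which does not secure a month-6 marrow. Section 3.3.1 itself only permits follow-up.

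The probabilities near 10% presuppose a patient who is both removed and MRD+. That objection stands: under the assumptions in step 6 the overall chance is around 1%. It also stands that the direction of bias is a conjecture. These patients may still have received cladribine, after which the plan assumes 65-75% are MRD-negative.

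A reader might infer that the trial plans to drop toxicity cases, that its intent-to-treat label is false, or that its power is misstated. The documents support none of these. Section 6.1 commits to analysis as randomised, though its example is early rituximab rather than a missing outcome, and both power figures reproduce.

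**Conclusion.** The contradiction between 3.3.2 and 3.8.2 is real and unconditional; the one with 3.3.1 and the DLT item of 3.8.1 depends on how 3.3.3 is read. Following 3.3.2 literally would produce loss of the primary outcome almost only in Arm 1.

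The effect is of unknown size and probably small. One lost MRD+ patient changes the conclusion in some configurations but leaves worst-case type I error within 10%; only two or more in a stratum exceed it. A reader might infer that the plan is biased towards rituximab. That is possible but not shown, since no outcome data for such patients are given. The point deserves correction because the loss is tied to treatment and can be avoided at little cost.

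**What to change.** - Reconcile 3.3.2 with 3.3.1, 3.3.3 and 3.8, so that stopping treatment for toxicity does not end collection of the 6-month MRD outcome already scheduled in Appendix A (15.1.3). No clinical stopping rule is proposed.
- In 6.1, state that all randomised patients are analysed as randomised, and name the rule that the main analysis uses for a result that is still missing.
- Report missing 6-month results by arm with reasons, and give observed-only and missing=MRD+ results as sensitivity analyses. The power loss in step 2 is why missing=MRD+ belongs there and not in the main analysis.
- Date the change. Section 6.3.1 already prints one MRD+ patient among 27 on immediate rituximab, so the rule should not appear to have been chosen after results were seen.

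Cost: changes of wording and no new visit. Patients who stopped treatment are asked to attend the scheduled assessment, including the marrow. Arm 1 results may look slightly less favourable.

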3.3.3 DLT criteria

Grade III-IV cladribine or rituximab related toxicity except:

- Grade 3-4 hematologic toxicity resolving in 2 weeks is not DLT.
- Grade 3 fever is not DLT.
- Grade 3 gastrointestinal toxicity for < 5 days is not considered DLT.
- Severe or life-threatening anaphylaxis or hypersensitivity reaction

